**Re: NCT05076370**

Attached please find the most recent protocol for the study, "Safety and Tolerability of Cannabidiol Among Persons with Opioid Use Disorder Receiving Methadone or Buprenorphine" (PI: [name]; NCT05076370).

The goal of the study is to examine the safety, tolerability, and efficacy of oral cannabidiol (Epidiolex) as an adjunctive treatment for persons with comorbid opioid use disorder and chronic pain who receive opioid agonist maintenance treatment.

This human laboratory crossover study will include a total of 40 participants across two consecutive phases: One open-label phase including 6 participants (NCT05076370), and one placebo-controlled phase including 34 participants (NCT04587791). We obtained initial approval for the open-label study on 07/02/2020, and continuing reapproval for the placebo-controlled phase on 04/17/2025.

In the open-label phase, we administered single doses of 400 mg, 800 mg, and 1200 mg of CBD, across 3 test sessions, using a dose-escalation paradigm. The open-label phase will ensure the collection of critical safety data and inform the subsequent placebo-controlled phase. The placebo-controlled phase will administer placebo, 400 mg, 800 mg, and 1200 mg of CBD, across 4 test sessions, in a random order. This study is conducted at the VA Connecticut Healthcare System and at Yale University and has been approved by the Institutional Review Board of both institutions (VA Connecticut Healthcare Human Subjects Subcommittee and Yale University Human Investigation Committee).

Attached please find the up-to-date study protocol. If you have any questions, please do not hesitate to contact me at [name] or at the email address provided in this letter.

Sincerely,

[name] [name].

**A. PRINCIPAL INVESTIGATOR:** [name] [name].\*

**B. CO-INVESTIGATORS:** [name]., Ph.D.\* , [name].\* , [name].\*

Authorized Prescribers: [name] [name]., [name]., Ph.D., [name]., [name]., [name].\* , [name].\*

Research Personnel: [name], R.N.\* , [name], B.S.W.\* , [name]\*, [name], M.S.\* , [name], B.A.\* , [name], B.S.\*

\* will have access to PHI and be able to obtain informed consent

**C. TITLE:** Cannabidiol Pharmacotherapy for Comorbid Opioid Use Disorder and Chronic Pain

**D. PURPOSE:**

The overarching goal of this study is to evaluate the potential of Cannabidiol (CBD) as an adjunctive treatment for comorbid opioid use disorder (OUD) and chronic pain. This is a randomized, placebo-controlled, crossover human laboratory study investigating the dose-dependent safety and acute effects of CBD on measures of pain and opioid craving in outpatients with OUD receiving medication-assisted treatment (MAT) with methadone or buprenorphine.

**D.1. Hypothesis:**

Treatment with CBD will be safe and well tolerated, and lead to improvement in vulnerability states that underlie the risk of relapse. Specifically, we hypothesize that:

a. *Primary Hypothesis:*

- Acute administration of CBD will be safe and well-tolerated by people with comorbid OUD and chronic pain who are on opioid agonist maintenance. Safety will be thoroughly measured with the Systematic Assessment for Treatment Emergent Events (SAFTEE) for adverse effects, the Drug Effects Questionnaire (DEQ) for abuse potential, and the Continuous Performance Test (CPT) and the Hopkins Verbal Learning Test (HVLT) for cognitive effects of CBD.

b. *Secondary Hypotheses:*

- Acute administration of CBD will lead to reduction of pain sensitivity, measured by assessments that include Quantitative Sensory Testing (QST) of thermal pain.
- Reduction of cue-induced craving and attentional bias to opioid cues, measured by assessments that include a visual probe task and the Heroin Craving Questionnaire (HCQ-14).

c. *Exploratory Hypotheses:*

- The above-mentioned effects will be influenced by the participants' biological sex.

**E. BACKGROUND:**

*E1. The need to develop novel treatments for comorbid OUD and chronic pain.* In the grip of the opioid crisis, it has been increasingly recognized that OUD and chronic pain have multiple points of interface. Growing evidence has shown that opioids increase pain sensitivity over time . Opioid craving and chronic pain also share clinical features and neuroadaptive traces that promote frequent relapse . Consequently, efforts to treat people with comorbid OUD and chronic pain have only been partially successful . Particularly among this population, opioid agonist maintenance may provide limited pain and craving relief . As result of inadequately treating these clinically relevant processes, the risk of relapse is increased.

While methadone is still a widely used medication for comorbid OUD and chronic pain, not only it is associated with pain hypersensitivity (hyperalgesia), but as a full opioid agonist, it causes dose-dependent gastrointestinal, cardiac, endocrine, and immune adverse effects – leading to lower quality of

life and high utilization of healthcare services. Collectively, these challenges highlight the need for novel therapeutics that can be used alone or in combination with opioid agonists.

*E2. The endocannabinoid (eCB) system as an emergent treatment target for comorbid OUD and chronic pain.* The endogenous opioid and the eCB systems share signaling pathways central to pain control and reward. Consistent with this notion, mounting preclinical data indicate that cannabinoids may curtail pain and opioid-seeking behavior. A meta-analysis of dozens of non-human primate and rodent studies showed that the opioid dose required to produce the same acute analgesic effect was up to 9.5 times lower, when co-administered with a cannabinoid agonist. Further, convergent research shows that cannabinoids may reduce opioid self-administration in animals made opioid-dependent. Importantly, these synergistic interactions between cannabinoids and opioids may be leveraged for treatment purposes, as their co-administration does not potentiate hypoactivity and respiratory depression.

*E3. Scientific evidence vs. public opinion regarding the therapeutic efficacy of cannabinoids.* To this date, 62% of U.S. states have authorized the use of cannabinoids for chronic pain. A growing number of states have also added OUD to the list of qualifying conditions. In stark contrast, treatment services for OUD and chronic pain often demand abstinence from cannabinoids as a sign of clinical stability. Such discrepancy accentuates the need for high-quality clinical research. In healthy humans, a meta-analysis of experimental studies indicates that cannabinoids increase pain threshold and tolerability, likely by influencing affect-related pain modulation in the central nervous system^19. Dysfunction in pain modulation is core feature of chronic pain, aggravating treatment refractoriness when OUD and chronic pain are comorbid. Yet, in disproportion to the clinical significance of the problem, thus far all prior studies investigating the efficacy of cannabinoids for pain relief excluded people with OUD. Only two studies examined the effects of oral delta-9-tetrahydrocannabinol (THC), the main psychoactive component of cannabis, on people with chronic pain on long-term opioid analgesic therapy (LTOT). Although these studies suggested synergistic analgesia between opioids and THC, it is not clear if the results are generalizable to chronic pain patients with OUD. Further, there has been some concern about the use of THC, a compound with abuse potential, among individuals with OUD. Hence, nearly all the evidence on how cannabinoids affect people with OUD is observational, and the effects of cannabinoids in comorbid OUD and chronic pain remain to be studied systematically.

*E4. Why Cannabidiol (CBD)?* CBD is a non-addictive cannabinoid with a wide safety margin – an especially important consideration for people with comorbid OUD and chronic pain. In 2018, CBD received FDA approval for treating rare forms of epilepsy. Since then, marked enthusiasm has mounted surrounding novel therapeutic applications, including chronic pain and OUD. CBD's anti-hyperalgesic and analgesic properties have been established across various preclinical models of pain (i.e., neuropathic, thermal, and inflammatory). Among the mechanisms proposed to account these properties is the suppression of brain- and spinal- mechanisms of central pain-sensitization. CBD is also believed to enhance affect-related pain inhibition in key brain areas responsible for modulating pain. Moreover, converging preclinical and human data indicate CBD's potential to reduce opioid craving and relapse. In a human laboratory study involving recently abstinent people with OUD, oral CBD (400 or 800 mg) reduced cue-induced opioid craving, with large effect sizes. Notably, cue-induced craving is a key mechanism in relapse that is not adequately treated by opioid agonist treatments. Altogether, CBD's pharmacological profile draws attention as a compelling two-pronged strategy to improve the treatment of people with comorbid OUD and chronic pain, who are heavily represented in populations receiving methadone maintenance.

Although CBD has been safely co-administered with fentanyl in humans, it has not yet been given with methadone or buprenorphine. The high prevalence of chronic pain among people receiving methadone and buprenorphine maintenance, combined with the frequent and controlled dispensation, offers advantages in terms of participant safety, feasibility, and recruitment.

Hence, this study will entail a human laboratory study establishing the safety of CBD in people with comorbid OUD and chronic pain who are on methadone or buprenorphine. This study will assess the effects of CBD on key treatment targets – pain sensitivity and cue-induced opioid craving. In this

manner, this study will yield information not only on the safety of CBD, but also on CBD's optimal analgesic and anti-craving dose for OUD and chronic pain.

*In summary, this study will evaluate the safety and efficacy of CBD for comorbid OUD and chronic pain, which cause extremely high morbidity and mortality nationwide. Since high pain sensitivity, cue-induced craving, and attentional bias for opioid cues increase the risk of relapse in this population, a human laboratory study will improve our understanding of the dose-related safety and efficacy of CBD to counteract these processes.*

## **F. SIGNIFICANCE:**

As outlined above, CBD has shown potential for improving several vulnerability states that underlie the risk of relapse. CBD's novel mechanisms of action as compared to the currently available drugs to treat OUD and chronic pain, and extremely favorable side effect profile, make it a compelling compound for investigation as novel agent to treat comorbid OUD and chronic pain – both to expand upon the currently available therapeutics and to limit the medical comorbidity associated with current therapies.

## **G. PARTICIPANTS:**

An initial safety pilot phase will recruit six participants: three receiving treatment with methadone and three receiving treatment with buprenorphine. If the results of the pilot study support the safety of CBD administration in this clinical sample, 75 participants will be enrolled for the general study with comorbid OUD and chronic pain, for a total of 34 completers – 22 subjects (11 men and 11 women) receiving methadone and 12 subjects (6 men and 6 women) receiving buprenorphine. This number of enrolled participants is expected to account for both screen fails and dropouts. Both sub-studies will enroll participants who do not currently require an inpatient hospitalization.

### **G.1. Inclusion Criteria:**

- Males and females, Veterans and non-Veterans, aged between 18 and 70 years old.
- Diagnosed with OUD and currently enrolled in methadone or buprenorphine maintenance treatment.
- Having chronic pain, uniformly operationalized as grade II (high-intensity) non-cancer pain for  $\geq 6$  months .
- Capable of providing informed consent in English.
- Compliant in opioid maintenance treatment and on a stable dose for four weeks or longer.
- Not meeting DSM-5 criteria for substance use disorders other than OUD or tobacco use disorder within the last 12 months.
- No current medical problems deemed contraindicated for participation by principal investigator.
- For women, not pregnant as determined by pregnancy screening; not breast-feeding; using acceptable birth control methods. Acceptable contraception for females includes oral contraceptives, contraceptive depot injections, contraceptive subdermal implants, intrauterine devices, or surgical contraception methods. Acceptable contraception for males includes condoms or surgical contraception methods.

### **G.2. Exclusion Criteria:**

- Other current major psychiatric disorders deemed clinically unstable by the principal investigator, such as severe depression and/or active suicidal ideation.
- Having experienced major psychosocial stressors recently ( $\leq 6$  weeks before enrollment), at the discretion of the principal investigator.
- Methadone dose under 30 mg or over 150 mg/day.
- Buprenorphine dose over 24 mg per day.
- Having received inpatient psychiatric treatment recently ( $\leq 60$  days before enrollment).
- Candidates receiving products containing either THC or CBD will be excluded. All participants will be asked to abstain from cannabinoids. Prior to receiving the study medication on the first test session, participants' cannabinoid use will be assessed using a quantitative point-of-care

urine 11-nor-9-carboxy-THC concentration test with a cut-off of  $\leq 50$  mg/mL. If a participant tests greater than  $\leq 50$  mg/mL, they will be asked to abstain for an additional 7 to 14 days. If 14 days after their initial THC concentration test the participant continues to test positive, they will not be allowed to participate in the study.

- A physician will carefully evaluate participants for use of over-the-counter or prescription psychoactive drugs known to affect pain threshold or pain tolerance (including NSAIDS, serotonin-norepinephrine reuptake inhibitors (SNRIs) (e.g. venlafaxine, duloxetine), gabapentinoids, tricyclic antidepressants (e.g., nortriptyline, amitriptyline), anticonvulsant medications (e.g., topiramate, carbamazepine)). Only participants who are on stable doses (i.e., consistent daily administration of the medication for at least three months at the same dose following the last dose change, either increase or decrease) of these medications, and whose dosing schedules allow participation in the study visits, thus excluding instances of single-dose or temporary dosing of the medication, will be eligible as determined by principal investigator. If possible, the morning dose will be administered after the study visit.
- Current, regular use of benzodiazepines, other prescription opioids, or platelet inhibitors (e.g., clopidogrel, apixaban, ticagrelor).
- Current weight of less of 60 kg.
- Allergy to sesame seed oil, which is an ingredient of the CBD formulation used.
- Serious medical or neurological illness or treatment for a medical disorder that could interfere with study participation as determined by principal investigator.
- Participants who have elevation of liver enzymes (ALT and/or AST) 2x above the normal limit or higher.

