such that the pharmacokinetics of CBD can vary widely, often without alteration in clinical effects. For instance, administering CBD with food may alter its pharmacokinetics, without significant change in its clinical effects: Among adults with epilepsy, in the fed state, the average Cmax of CBD was 14 times higher, and the AUC0 - ∞ was 4 times higher, compared to the unfed state; conversely, the antiseizure, neuropsychological, and safety profile of CBD remained unchanged in both conditions . Fourth, the relationship between the clinical – or pharmacodynamic – effects of drugs and their pharmacokinetic properties are often non-linear. This is especially true for highly lipid soluble drugs like cannabinoids, including THC and CBD. For example, although THC metabolites stay in the organism for several days or weeks – THC's elimination half-life ranges from 25 to 36 hours –, clinical effects like analgesia or sedation last only several hours.

As a result, cannabinoids like THC and CBD are often administered twice daily when used clinically, rather than once every 3 to 4 days, as if the pharmacokinetic and clinical effects were linear. We have an ongoing randomized, placebo-controlled, within-subject human laboratory study administering single doses of oral THC (10 mg or 20 mg) to persons with opioid use disorder treated with methadone, also has an interval of 72 hours between test sessions.

The latter study has been recently reviewed and approved by the VA HSS (MS0056) and the Yale IRB (Protocol # 2000027065; NCT04025359). Fifth, prior studies conducted at our center suggest that a longer interval is likely to increase attrition of the study population – persons with comorbid opioid use disorder and chronic pain –, such that data collection may be compromised. Finally, we are considering the pharmacokinetic effects of CBD on the main study outcomes, as exemplified by the repeated measurements of CBD and opioid levels in our protocol. Notably, both the FDA and NIDA are in accordance with the proposed interval of 72 hours.

For the general study Research Pharmacy will create a randomization sheet for this general study. Both the research team and participants will be blind to the randomization.

An Environmental Assessment is not required because the action requested qualifies for a categorical exclusion per 21 CFR 25.31(e). To the applicant's knowledge, no extraordinary circumstances exist per 21 CFR 25.15(d).

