**M.5. Psychiatric Evaluation and Study Assessments (Pilot and General Studies):** It is worth noting that our participants will be recruited exclusively from OTPs, which provide both psychiatric and addiction treatment. Participants will be seen every 3 days for 4 experimental sessions. Before each experimental session, participants will be required to refrain from consuming alcoholic beverages and drugs during study participation, which will be verified by urine drug screening and breathalyzer measurements before the sessions. If results indicate non-adherence with these study procedures, the session will be rescheduled. Repeatedly non-adherent participants will be discharged from the study. Since our participants are provided with a light snack before each test session, and a small meal at the

end of each test session, we ask our participants to not eat after midnight on the day of your test sessions. However, you can drink your usual amount of coffee or caffeinated beverage before each test session.

A physician and a member of the research team will be present with the participants during all the testing, monitoring participants' comfort with all study procedures, using equipment that adheres to local institutional safety standards. Participants will be informed that they can take breaks or withdraw (themselves and their data) from the study without justification at any time. After testing, study staff will inquire about the participant's general well-being. Participants will be made aware that, if they experience a clinically significant worsening of mood symptoms, or if active suicidal ideation emerges, they will be escorted to the nearest psychiatric emergency room.

A physician will conduct a thorough evaluation before discharge after each experimental session. Participants may be observed until craving subsides. In the event participants test positive for non-medical substance use or breathalyzer indicate recent alcohol use, the experimental sessions will be rescheduled until clinical stability is ensured. Regular treatment with opioid agonists will be continued during the study. One week after completing the four experimental sessions, participants will be contacted by telephone for another safety follow-up.

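### The urine THC-metabolite check before the first test session uses a cut-off of 50 mg/mL, which no urine sample can reach, so that check can never defer or exclude a participant

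*Combined protocol and SAP*

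**What the plan says.** The rule is in the protocol, section G.2 (Exclusion Criteria). Before study medication at the first test session, participants have a "urine 11-nor-9-carboxy-THC concentration test with a cut-off of" at most 50 mg/mL. The next sentence deals with a result over that limit. It repeats the unit and puts a less-than-or-equal sign directly after the words for exceeding it: "mg/mL, they will be asked to abstain for an additional 7 to 14 days". The last step applies 14 days after the initial test: if "the participant continues to test positive, they will not be allowed to participate in the study".

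The cut-off cites references 146 and 147; the reference list in section T ends at 87. No other THC threshold or unit appears in the documents.

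Several provisions bear on cannabinoid use without using this cut-off:

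- G.2, opening of the same bullet: "Candidates receiving products containing either THC or CBD will be excluded".
- G.1: "Not meeting DSM-5 criteria for substance use disorders other than OUD or tobacco use disorder within the last 12 months".
- K.2 and M.1.2: urine toxicology at screening, and a drug use history.
- K.6 and the session schedule in K.8: a calendar-based record of drug use, and urine drug testing at each session's baseline.
- M.5: "In the event participants test positive for non-medical substance use or breathalyzer indicate recent alcohol use, the experimental sessions will be rescheduled", and "Repeatedly non-adherent participants will be discharged from the study".

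**The concern.** This is a numeric eligibility rule that staff are expected to apply. If no sample can exceed the limit, the three-step procedure (test, deferral, exclusion at 14 days) does nothing, and a participant with recent or undisclosed use passes in the same way as one with none.

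That matters in a single-dose cannabinoid study. Section E3 reports that cannabinoids raise pain threshold in healthy people and that THC studies suggested synergistic analgesia with opioids. Pain sensitivity is a secondary outcome here, and cognition and adverse effects belong to the primary safety hypothesis (D.1). Section K.4 notes that THC metabolites persist for days or weeks, so the position of the threshold decides who counts as positive. Cannabis use frequency enters the analysis only as a covariate to be explored (K.10), which does not replace a working check at entry.

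**Working it through.** The cut-off is a stated threshold and not a derived figure, so there is no calculation of the plan's to reproduce. The question is whether a urine sample could reach it.

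**Inputs from the protocol**
- Cut-off C = 50 mg/mL (G.2, stated twice).
- Scale of a THC dose D = 10 or 20 mg. K.4 describes another study by the same group "administering single doses of oral THC (10 mg or 20 mg) to persons with opioid use disorder treated with methadone".

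**Assumptions not in the documents**
- Volume of one void V: 50 to 2,000 mL.
- Mass of metabolite per unit mass of THC, r: 1.0 to about 1.1 (1.095 used for the upper value).
- Deliberately extreme case: the whole dose becomes this metabolite and leaves in a single void.

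**Step 1: convert the unit.** 50 mg/mL × 1,000 mL/L = 50,000 mg/L = 50 g/L, or 5% weight/volume.

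**Step 2: compare one millilitre with one dose.** 50 / 20 = 2.5 and 50 / 10 = 5. One millilitre at the cut-off holds 2.5 to 5 whole doses.

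**Step 3: mass needed in a sample, C × V.**
- 50 mL: 50 × 50 = 2,500 mg = 2.5 g, the mass of 2,500 / 20 = 125 doses of 20 mg.
- 250 mL: 50 × 250 = 12,500 mg = 12.5 g, the mass of 12,500 / 20 = 625 doses of 20 mg.

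**Step 4: highest concentration from one 20 mg dose, D × r / V.**

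| Void volume | r = 1.0 | r = 1.095 | Cut-off divided by result |
|---|---|---|---|
| 50 mL | 0.40 mg/mL | 0.438 mg/mL | 125 to 114 |
| 250 mL | 0.08 mg/mL | 0.088 mg/mL | 625 to 571 |
| 2,000 mL | 0.010 mg/mL | 0.011 mg/mL | 5,000 to 4,566 |

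**Step 5: volume in which the whole dose would sit at the cut-off, D × r / C.** 20 × 1.0 / 50 = 0.40 mL; 20 × 1.095 / 50 = 0.44 mL.

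**Heavier use than one dose.** By the 50 mL row of Step 4, 114 to 125 doses of 20 mg would have to be wholly excreted as this metabolite in one small void. Larger voids need more, so heavy use does not bring the limit within reach.

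**The case against.** Two readings go further than the documents allow.

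A reader might infer that the cannabinoid exclusion as a whole excludes nobody. It does not follow. The opening sentence of the same bullet excludes candidates receiving THC or CBD products without any test. G.1 removes anyone with a cannabis use disorder in the past 12 months. Screening toxicology, baseline drug testing at each session, and the rescheduling and discharge rules in M.5 do not use the 50 mg/mL figure either. All of this stands. It does not fully replace the quantitative check: the product exclusion states no objective test, G.1 does not cover use without a disorder, and the documents neither list the substances in the urine drug screens nor give them a THC threshold.

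A reader might also infer that the unit error lets residual THC vary between sessions and so mimic or mask CBD effects. The check is tied to the first test session. With a correct unit it would still not track sessions 2 to 4; the provisions aimed at those sessions are in K.8 and M.5, which the error does not touch. Dose order is randomised and counterbalanced, and session order is to be considered in the models (K.10), so residual THC unrelated to dose order would mainly add noise.

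The unit is probably a slip, and staff with a real assay would likely notice it. The out-of-range references suggest text carried over from elsewhere. But the protocol offers no figure to fall back on. Staff would have to depart from a written eligibility rule and use a threshold that is not in it.

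**Conclusion.** The point holds for the quantitative urine check and no further. As written, the check, its 7 to 14 day deferral and its exclusion at 14 days never trigger. The margin is at least about 114-fold in the extreme case shown. That multiple rests on the assumed void volume and mass ratio, but the conclusion does not: one millilitre at the cut-off already holds 2.5 times a whole 20 mg dose.

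Participants with undisclosed or residual cannabinoid use can pass the only quantitative THC check in the protocol. How many would do so, and what it would do to the pain, craving, sedation or cognitive results, cannot be calculated from the documents. Alpha, power and the sample size of 34 are unaffected.

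The comparison is garbled as well, and the two cited sources are absent from the reference list. The same unit appears in both places, which points to an error in the protocol. If the sponsor's source file shows a different unit, that part falls away, and the wording and the references still need attention. The threshold is wrong as written and should be corrected.

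**What to change.** In G.2:

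- Reconcile the unit and value with what the point-of-care assay reports. The documents do not contain the intended unit, so it must come from the assay's instructions.
- State the rule once with a clear direction, for example that a result above the stated limit is positive, and remove the contradictory sign.
- Say that the retest at 14 days uses the same limit.
- Correct citations 146 and 147, or add the missing sources to section T.

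Reconcile G.2 with M.5: say whether the session drug screens include THC and, if so, what counts as positive there. Otherwise the same participant could pass under one section and be rescheduled under the other.

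If participants have already been tested, record which limit was actually applied.

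The cost is a short text amendment, with no added participants, visits or procedures.
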